1. INTRODUCTION

The final version (version 2.0) of Statistical Analysis Plan (SAP) for KPL-914-C002 study, based on the Protocol version 3.0 Amendment #2 dated 10MAR2020, was signed off on 16JUN2020. The statistical rules, efficacy and safety endpoints for long-term extension (LTE) period have been specified in SAP version 2.0. As a supplemental document, this addendum only summarizes key additional analyses, analyses planned but not conducted for LTE period in SAP V2.0 due to changes in business or scientific interests, or due to data availability.

2. ADDITIONAL ANALYSES

2.1 LTE 18-Month

LTE 18-month is the visit at 18 months after their most recent recurrence, (i.e., the qualifying episode for their original study enrollment prior to enrolling in the RI period or a recurrence in RW which was treated with bailout rilonacept, whichever is the later).

If LTE 18-month visits are collected in CRF, those visits in CRF will be used for analyses. Otherwise, LTE 18-month visits will be mapped based on the visit date on LTE 18-month disposition with 60 days window. The closest assessments will be mapped. If two visits have the same distance, the later one will be used.

In addition to treatment disposition and study disposition, disposition of LTE 18-month will be summarized as well:

- Continue treatment with open-label KPL-914
- Continue in study off-treatment for observation (with option to re-initiate open-label KPL-914 on-study if there is a pericarditis recurrence)
- Discontinue from the LTE
 - Patient decision
 - Investigator's decision
 - No inflammation on MRI
 - Other

For subjects who decided to continue in study off-treatment for observation, the following parameters will be summarized:

- Time on observation: defined as minimum (first dose date after observation-1, EOS date) – disposition date of off-treatment for observation +1.
- Days on treatment before entering observation, defined as: (disposition date of off-treatment for observation-1) - first dose date of LTE period +1.
- Days on treatment after observation for subjects who entered observation and later resumed treatment: minimum (last dose date after observation +6, EOS date) - first dose date after observation + 1.

For the subgroups of subjects who decided to continue in study off-treatment for observation and subjects continue treatment with open-label KPL-914, additional analyses will be conducted.

- Time to recurrence from LTE 18-month will be defined from LTE 18-month disposition date to recurrence or censored at last assessment before treatment resumed or end of study whichever is first.
- Annualized incidence of recurrence after LTE 18-month visit will be defined as number of recurrences for all patients divided by sum of subject-years for all patients within each subgroup. Denominator will be calculated as below:

For subjects who decided to continue in study off-treatment for observation

- If subjects resumed treatment, first dose date after observation period – LTE 18-month disposition date
- If subjects never resumed treatment, EOS date – LTE 18-month disposition date +1

For subjects who continued treatment with open-label KPL-914,

- EOS date – LTE 18-month disposition date +1.

The 95% CI will be calculated using an exact method with Poisson distribution.

- Line plots of PGIPS, PGAPA, CRP over time will be provided as well.

For all subjects treated in LTE period, annualized incidence of recurrence from LTE baseline to LTE 18-month will be summarized. Denominator of subject years will be summarized from LTE first dose date to the minimum of End of study date, , LTE 18-month date-1.

2.2 Adverse Events

Two additional summaries of adverse events will be conducted:

- In addition to summarizing treatment-emergent adverse events, post-treatment adverse events will also be summarized. Post-treatment adverse events are defined as adverse events that started after the last dose of study drug in LTE period + 6 weeks.
- Upper respiratory infection adverse events will be summarized. Upper respiratory infection will be identified by the following preferred terms: Nasopharyngitis, Pharyngitis, Pharyngitis streptococcal, Rhinitis, Sinusitis, Upper respiratory tract infection and Viral upper respiratory tract infection.

3. CHANGES TO THE PLANNED ANALYSES

3.1 Efficacy Endpoints

Changes to the analyses for the LTE Efficacy endpoints specified in SAP version 2.0 (section 5.3.2.3) are listed below:

Efficacy endpoints	Changes	Reason
--------------------	---------	--------

2. Proportion of subjects with Clinical Response (rilonacept monotherapy + $CRP \leq 0.5$ mg/dL + $NRS \leq 2$) at each CRP assessment (weeks 12 and 24). The pain NRS at the visit when CRP was assessed will be used. subjects randomized to KPL-914 utilizing pooled data in RW and LTE periods and there will be no hypothesis testing.	Not done	NRS scores were collected only upon pericarditis recurrence.
4. Change over time in pericarditis pain NRS.	Not done	NRS were collected only upon pericarditis recurrence.
14. Corticosteroid use over time. For subjects who are on corticosteroid at RI baseline, the proportion of subjects using corticosteroid at LTE will be summarized. The denominator will be the number of subjects using corticosteroid at RI and entering the LTE. The average daily dose of corticosteroid (mg/day) will be summarized.	Not done	Only limited data available as corticosteroid use is allowed only as rescue medication

3.2 Safety Endpoints

Summaries of safety endpoints are conducted by study period (RI, RW, and LTE period) only.

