5.3. Safety Analysis

The following safety endpoints will be analyzed:

- Adverse events,
- Clinical laboratory parameters,
- Serology parameters,
- Hematology parameters,
- Non-fasting lipid panel,
- Pregnancy test,
- Vital signs,

- Urinalysis,
- Electrocardiogram, and
- Physical examination.

Descriptive statistics will be used to summarize safety endpoints for all subjects by the following periods:

- RI period (KPL-914)
- RW period
 - KPL-914 vs. Placebo Including Bailout Rilonecept
 - KPL-914 vs. Placebo before Bailout Rilonecept
- LTE period
- Study overall (RI through LTE), KPL-914 or placebo, regardless of receiving bailout Rilonecept.

Two-sided 95% CIs will be presented where meaningful. Data summaries will be displayed for clinical laboratory analyses, vital signs measurements, ECGs, and physical examination findings.

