5.3.1. Adverse Events

Treatment-emergent AEs (TEAEs), defined as AEs that start or increase in severity after the first dose of study drug and before 6 weeks after the last dose of study drug, will be coded to system organ class and preferred term using MedDRA v21.1.

TEAEs will be summarized by each period and study overall. In the RW period, they will also be summarized by including and excluding bailout rilonecept, respectively. The average follow-up duration in weeks for TEAE will be provided in summary tables. The duration of follow-up for each subject is defined as follows.

- For the RI period, it is from first dose in RI period until the day before randomization, last dose day plus 6 weeks, last study day, or data cutoff, whichever occurs first.
- For the RW period including bailout, it is from randomization to data cutoff, last dose day plus 6 weeks, or last study day, whichever occurs first.
- For the RW period before bailout, it is from randomization to the start of using bailout rilonecept, data cutoff, last dose day plus 6 weeks, or last study day, whichever occurs first.
- For the LTE period, it is from first dose day in LTE period to data cutoff, last dose day plus 6 weeks, or last study day, whichever occurs first.
- For study overall, it is from first dose day in RI period to data cutoff, the last dose plus 6 weeks, or last study day, whichever occurs first.

A summary of the frequency (number and percentage of subjects) of TEAEs will be presented by system organ class and preferred term. Adverse events will also be analyzed by their severity (mild, moderate or severe), relationship to study drug, serious AEs, AEs leading to death, AEs resulting in dose interruption, AEs leading to withdrawal of study treatment, and AEs of injection site reaction.

Any AE of malignancy (excluding basal cell carcinoma of the skin) is of special interest. AE of special interest will also be summarized.

A subject experiencing the same AE multiple times will be counted only once for that preferred term. Similarly, if a subject experiences multiple AEs (preferred terms) within the same system organ class, then that subject will be counted only once for that system organ class. When summarizing by severity and relationship, only event with highest severity or relationship will be counted. All AEs will be presented by SOC and preferred terms.

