Incidence rate per 100 subject-years and its 95% CI will be calculated by the periods defined for follow-up duration above for the following groups of AEs:

- All AEs (include any AE),
- SAE (include any SAE),
- deaths,
- all infections (including serious),
- serious infections (serious only),
- all ISR (injection site reaction, including serious and non-serious),
- only serious ISR,
- all malignancies excluding NMSC (Non-Melanoma Skin Cancer: ie. cutaneous basal cell carcinoma and cutaneous squamous cell carcinoma).

Incidence rate per 100 subject-years = $100 \times (\text{number of different AE start days within the treatment period}) / (\text{Sum of treatment duration in years from all subjects in the cohort})$.

Multiple events within a subject will be counted as multiple events. Treatment exposure duration and follow-up of AE's in the Study Overall period will be 6 weeks after the last dose. There will be no formal hypothesis testing.

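### The addendum drops the study-overall safety summary without a specific reason, so the whole-study share of subjects with a serious event can only be bounded

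*SAP*

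**What the plan says.** SAP v2.0 Section 5.3 lists the groupings for every safety endpoint: RI, RW (including and before bailout), LTE, and a fourth, "Study overall (RI through LTE), KPL-914 or placebo, regardless of receiving bailout" rilonacept. Section 5.3.1 repeats this for adverse events: "TEAEs will be summarized by each period and study overall". It gives the fourth grouping its own follow-up window: "For study overall, it is from first dose day in RI period to data cutoff", the last dose plus six weeks, or the last study day, whichever comes first.

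Two counting rules in Section 5.3.1 matter here. For subject percentages, "A subject experiencing the same AE multiple times will be counted only once for that preferred term", and likewise once per system organ class. For incidence rates, "Multiple events within a subject will be counted as multiple events", and the denominator is the "Sum of treatment duration in years from all subjects in the cohort".

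The addendum, under its heading for changes to planned analyses, then says in Section 3.2: "Summaries of safety endpoints are conducted by study period (RI, RW, and LTE period) only". The sentence does not name the study-overall summary, but a list of three periods closed by the word only leaves no place for it. Addendum Section 3.1 gives a reason for each efficacy endpoint not done; Section 3.2 gives none.

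**The concern.** Safety is the study's secondary objective (SAP v2.0 Section 1.1.2). A basic question under it is what proportion of treated subjects had a serious event, a serious infection or a malignancy at any time from first dose to the end of the LTE. The study-overall table would have answered it. Period tables cannot, because a subject with an SAE in RW and another in LTE appears in both, and nothing in the two tables shows that it is the same person.

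The primary analysis does not fill the gap. Section 2.4 excludes the LTE from it, so any study-overall table produced at that cutoff leaves out up to 24 months of open-label treatment.

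**Working it through.** The plan gives no safety counts, so there is no stated figure to reproduce. The check asks which whole-study quantities follow from the period tables.

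**Inputs.** Planned enrolment of about 56, of whom about 50 are randomized (Section 2.3.1). Counting rules and follow-up windows (Section 5.3.1). Exact Poisson interval (Section 13.4). All event counts and LTE durations below are assumptions.

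**1. Share of distinct subjects.** If *a*, *b* and *c* subjects have the event in RI, RW and LTE, and *N* were treated, the number of distinct subjects *U* satisfies

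max(*a*, *b*, *c*) ≤ *U* ≤ min(*N*, *a* + *b* + *c*).

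With *N* = 56:

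| Assumed RI / RW / LTE | Lowest *U* | Highest *U* | Range of share |
|---|---|---|---|
| 1 / 2 / 3 | 3 | 6 | 3/56 = 5.4% to 6/56 = 10.7% |
| 2 / 4 / 6 | 6 | 12 | 6/56 = 10.7% to 12/56 = 21.4% |
| 3 / 6 / 9 | 9 | 18 | 9/56 = 16.1% to 18/56 = 32.1% |

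The upper bound is at most three times the lower, and reaches that when the three counts are equal.

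**2. Pooled rate.** Every event counts and person-time is summed, so for periods that do not overlap

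pooled rate = 100 × (sum of events) / (sum of subject-years).

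In one simulated set of 56 subjects with disjoint periods, 3 + 1 + 11 = 15 events over 112.9 subject-years gave 13.28 per 100 subject-years, the same as the direct whole-study calculation. In that set the subjects affected per period were 3, 1 and 10. These sum to 14, against 13 distinct subjects. The rate was recovered exactly and the subject count was not.

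The Section 13.4 interval needs only total events and total subject-years. For the SAP's own example call (14 events, 400 subject-years) the rate is 100 × 14/400 = 3.5, with 95% CI 1.913 to 5.872.

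**3. Overlap of RW and LTE windows.** RW follow-up ends at the first of data cutoff, last dose plus six weeks, or last study day. Cutoff comes after all subjects have had their end-of-RW visit (Section 2.4), and that visit is also the LTE baseline. RW follow-up can therefore run past the first LTE dose. Assume 50 subjects overlap by up to six weeks:

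- Double-counted time: 50 × 6/52.18 = 5.75 subject-years.
- Total time, assuming 12 weeks of RI in 56 subjects, 24 weeks of RW in 50, and 1 to 2 years of LTE in 50: 12.9 + 23.0 + 50 = 85.9, up to 12.9 + 23.0 + 100 = 135.9 subject-years.
- Person-time overstated by 5.75/135.9 = 4.2% to 5.75/85.9 = 6.7%.

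An event in the overlap could also be counted twice. If the denominators are instead the Section 5.1.6 treatment durations, the overlap is about one day per subject: 50 × (1/7)/52.18 = 0.14 subject-years, or 0.1% to 0.2%.

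**4. Exposure.** Section 5.1.6 summarizes treatment duration, number of administrations, compliance and total rilonacept dose for each period and for the study overall. Addendum 3.2 speaks of safety endpoints, and study drug administration is not on the Section 5.3 list of those, so this summary stays.

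**The case against.** The case for leaving the addendum alone has real substance.

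- *Rates survive.* A reader might infer that the pooled incidence rate, and the precision that comes from all exposure time, are lost. They are not: step 2 rebuilds the rate, exactly if windows are disjoint. This objection stands, except that someone must do it by hand and allow for the RW/LTE overlap.
- *Exposure survives.* A reader might also infer that nothing shows rilonacept exposure from first dose to last. Section 5.1.6 still does.
- *The dropped table was not a rilonacept table.* Section 5.3 pooled KPL-914 and placebo time, so reinstating it would not by itself give risk over rilonacept exposure. This stands.
- *For very rare events the bounds are tight.* Deaths add exactly, since a subject dies once. With counts of 0, 1 and 1 the answer is one or two subjects (1/56 = 1.8% or 2/56 = 3.6%). The ambiguity grows with the number of affected subjects. Section 3.1 also promises data listings, from which distinct subjects may be identifiable. This limits the size of the problem, but a listing does not replace a planned summary.
- *A reason of sorts exists.* The addendum's introduction cites changes in business or scientific interest, or data availability, for all dropped analyses. That is generic. Data availability is not an evident explanation here, because an overall table uses the same adverse-event records as the period tables.

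**Conclusion.** The point holds in a limited form. Addendum 3.2 removes a planned whole-study safety summary without a specific reason. What is lost is the proportion of distinct subjects with a TEAE, SAE, serious infection or malignancy from RI through LTE, which period tables fix only to within a factor of up to three. The 10.7% to 21.4% range rests on assumed counts of 2, 4 and 6 and on planned enrolment of 56; it illustrates the width and does not predict results.

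The documents do not support going further. Pooled rates can be rebuilt approximately, with person-time overstated by 4.2% to 6.7% under the six-week overlap assumption and by far less under treatment-duration denominators. This is a reporting gap that should be closed; it does not make the safety data uninterpretable.

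**What to change.** Amend Addendum Section 3.2 to keep, beside the period tables, one study-overall table of subjects with TEAEs, SAEs, serious infections, malignancies and deaths. Report with it the Section 5.3.1 incidence rates over the single study-overall window, which counts each event and each day once and so removes the RW/LTE overlap.

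Preferably add a column restricted to rilonacept-exposed time: RI, the rilonacept arm of RW, bailout, and LTE. This would be a new analysis, because the v2.0 summary included placebo time. It needs a written exposure window, including how events in the six weeks after a last rilonacept dose are attributed when a subject moves to placebo.

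The basic table costs one extra table set from adverse-event data already collected, plus a sentence in the addendum. The rilonacept-only column costs the derivation of its window. If the sponsor still prefers to omit the summary, Section 3.2 should say why, as Section 3.1 does for the efficacy endpoints, though that would leave the whole-study share unreported.

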ECHO	echocardiography; echocardiogram
eCRF	electronic case report form
EDC	electronic data capture
EORW	End of Randomized Withdrawal (visit)

Abbreviation	Definition
EOT	End of Treatment (visit)
EQ-5D-5L	5-level EuroQoL-5D
ESR	erythrocyte sedimentation rate
FDA	US Food and Drug Administration
GI	gastrointestinal
HDL	High density lipoprotein
HIV	human immunodeficiency virus
ICF	informed consent form
ISI	Insomnia Severity Index
ISR	injection site reaction
ITT	intent to treat
IV	intravenous(ly)
IWRS	interactive web response system
KM	Kaplan-Meier
KPL-914	rilonacept
LDL	Low density lipoprotein
LTE	Long Term Extension Treatment Period
MedDRA	Medical Dictionary for Regulatory Activities
cMRI	cardiac magnetic resonance imaging
MRI	magnetic resonance imaging
NMSC	Non Melanoma Skin Cancer
NSAID	nonsteroidal anti-inflammatory drug
NRS	Numerical Rating Scale
ORT	Oral Rescue Therapy
PGA-PA	Physician Global Assessment of Pericarditis Activity

Abbreviation	Definition
PGIPS	Patient Global Impression of Pericarditis Severity
PK	pharmacokinetic(s)
POC	point of care
RE	Role participation with emotional health problems in SF-6D
RI	Run-In (period)
RP	Role participation with physical health problems in SF-6D
RW	Randomized Withdrawal (period)
SAE	serious adverse event
SAP	Statistical Analysis Plan
SAS	Statistical Analysis System
SC	subcutaneous(ly)
SF-36	36-Item Short Form Health Survey
SFU	safety follow up
SOC	standard of care
TEAE	Treatment emergent adverse event
ULN	upper limit of normal
WBC	white blood cell

1. STUDY OBJECTIVES

1.1. Study Objectives

1.1.1. Primary Objective

The primary objective of this study is to assess the efficacy of rilonacept treatment in subjects with recurrent pericarditis.

1.1.2. Secondary Objectives

The secondary objective of this study is to assess the safety of rilonacept treatment in subjects with recurrent pericarditis.

2. STUDY DESIGN

2.1. Design Overview

This study has the following periods:

- **Screening period**, during which assessment of disease characteristics, baseline therapy, and the pretreatment workup is completed (up to 4 weeks).
- **Single-blind Run-In (RI) period** (12 weeks), during which blinded rilonacept is administered subcutaneously (SC) once weekly in all subjects after the loading dose of double injections. The RI period includes the following:
 - 1-week Stabilization period, during which blinded rilonacept is administered in addition to standard of care (SOC) pericarditis therapy and the ongoing pericarditis episode is treated.
 - 9-week Weaning period, during which subjects are weaned off background SOC pericarditis therapy, as applicable, while treatment with blinded rilonacept continues.
 - 2-week Monotherapy period during which subjects who have successfully weaned off background SOC pericarditis therapy will continue to receive blinded rilonacept.

In the single blind RI period (subjects are blinded regarding the time of transition from the single- blind to the double- blind- period), adult subjects ≥ 18 years old will receive rilonacept as an initial loading dose of 320 mg (2 SC injections of 160 mg each) at the RI baseline visit (2×2 mL), followed by a 160 mg (2 ml) SC dose once weekly throughout the RI period. Pediatric subjects (≥ 12 and < 18 years old) will receive an initial loading dose of rilonacept 4.4 mg/kg (2 SC injections of 2.2 mg/kg each) at the RI baseline visit (maximum 2×2 mL), and then 2.2 mg/kg (maximum 2 mL) SC once weekly throughout RI period.

Subjects who achieve clinical response at RI Week 12 defined as stopping background pericarditis therapy no later than Week 10 and weekly average of daily pericarditis pain score ≤ 2.0 on the 11-point Numerical Rating Scale (NRS) within the 7 days prior to and including the day of randomization on RI Week 12/Randomization Withdrawal (RW) baseline and a C-reactive protein (CRP) level ≤ 0.5 mg/dL at the RI Week 12/RW baseline visit, will proceed into the double-blind placebo-controlled RW period.

Subjects who do not achieve clinical response at RI Week 12/RW baseline on rilonacept monotherapy will be discontinued from study drug, transitioned to SOC pericarditis therapy at the Investigator's discretion and followed through the end of the RW period.

Additionally, after the randomized withdrawal period has been closed when at least 22 confirmed recurrent pericarditis events have been accrued, subjects who have not yet completed the full 12 weeks of RI period at that time will be allowed to continue tapering of concomitant meds in the RI period; those subjects who achieved clinical response by Week 12 will be given the option to receive open-label rilonacept in the Long-term Extension Treatment period (LTE) without having to proceed through the RW period.

- **Double-blind placebo-controlled RW period** (pericarditis recurrence event-driven duration), during which subjects who were able to stop background SOC pericarditis therapy and who achieve clinical response at RI Week 12/RW baseline are randomized in a double-blind manner at a 1:1 ratio to the following:
 - Rilonacept 160 mg (2.2 mg/kg in pediatric subjects) SC injections once weekly
 - Matching placebo SC injections once weekly

Pericarditis Recurrence in the RW Period

Pericarditis recurrence is defined as the recurrence of typical pericarditis pain associated with supportive objective evidence of pericarditis. Upon pericarditis recurrence, subjects who report at least 1 day with pericarditis pain measurement ≥ 4 on the 11 point NRS and have 1 CRP value ≥ 1 mg/dL (either on the same day or separated by no more than 7 days) will receive bailout rilonacept (2 open-label injections of 160 mg rilonacept [or 4.4 mg/kg for pediatric subjects] followed by once weekly open-label rilonacept SC injections of 160 mg [or 2.2 mg/kg for pediatric subjects]) irrespective of randomized treatment assignment and as soon as at least 5 days have passed since the last study drug injection. Sequential oral rescue therapy (ORT), i.e., analgesics first, then NSAIDs, and then colchicine, can be added if needed at the discretion of the Investigator, as outlined in the protocol and Pharmacy Manual.

Subjects with pericarditis recurrence and who do not meet the protocol criteria for bailout rilonacept will continue blinded study drug until the protocol criteria for bailout rilonacept are met or through the end of the RW period. For those subjects, sequential ORT can be added to blinded study drug at the discretion of the Investigator, as outlined in the protocol and Pharmacy Manual.

All suspected pericarditis recurrence events in the RW period will be formally adjudicated by the Clinical Endpoint Committee (CEC), and only events that are confirmed by the CEC as pericarditis recurrences will be used in the Primary Endpoint analysis.

- **Long-term Extension Treatment period (LTE)** (variable, up to 24 months), during which all subjects in the RW period (including subjects transitioned to open-label rilonacept upon pericarditis recurrence) and subjects who are in the Run-In period after closure of the RW period, will have an option to receive up to 24 months of open-label rilonacept 160 mg (or 2.2 mg/kg for pediatric subjects) SC injections once weekly based on their clinical status and at the discretion of the Investigator, after signing LTE informed consent.

Subjects will be reviewed at 18 months after their most recent recurrence, (i.e., the qualifying episode for their original study enrollment prior to enrolling in the RI

period or a recurrence in RW which was treated with bailout rilonacept, whichever is the later). During this month visit, the Investigator and subject will decide whether to continue treatment with open-label rilonacept, to continue in the study off-treatment for observation and rilonacept bailout upon subsequent recurrence, or discontinuation from the LTE. This review may be supplemented by:

- cMRI and/or echocardiogram and/or additional diagnostic testing as determined by the Investigator.
- subjects may be unblinded at that time (if available) at the request of the Investigator per procedures outlined in the Unblinding Plan to assist in clinical decision-making.

Safety data will be reviewed throughout the LTE by the Data Monitoring Committee.

